5.2.2 Subject Disposition

The number and percentage of subjects who discontinue the study treatment will be tabulated, along with the primary reason for discontinuation.

5.2.3 Protocol Deviations

Protocol deviations will be determined prior to database lock. The protocol deviations data as collected in the clinical database will be presented in tables and/or listings as appropriate.

5.2.4 Demographic and Other Baseline Characteristics

Demographic and other baseline characteristics will be summarized for the FAS using descriptive statistics. They will include age (year), age group, race [White, Black or African American, Asian (Japanese, Chinese, Other Asian), American Indian or Alaska Native, Native Hawaiian or other Pacific Islander, and Other], ethnicity (Hispanic or Latino, not Hispanic or Latino), height (cm), weight (kg), and BSA (body surface area), as well as Karnofsky performance score (for subjects >16 years of age) or Lansky play-performance score (for subjects ≤16 years of age). Cancer history and prior anticancer therapies will be summarized.

For continuous variables, the number of non-missing observations, mean, standard deviation, median, 25th percentile (Q1), 75th percentile (Q3), minimum, and maximum will be presented. For categorical variables the number and percentage of patients will be presented.

MEDICAL HISTORY

The number and percentage of subjects reporting a history of any medical condition will be summarized for the FAS. Listing of medical history will be provided.

5.2.5 Prior and Concomitant Therapy

All investigator terms for medications recorded in the CRF will be coded to an 11-digit code using the World Health Organization Drug Dictionary (WHO DD) 2017 or current (WHODDMAR18_HD_B2). The number (percentage) of subjects who have taken prior and concomitant medications will be summarized by Anatomical Therapeutic Chemical (ATC) class (ie, anatomical class, therapeutic class) and WHO drug preferred term. Prior medications will be defined as medications that stopped before the first dose of study drug. Concomitant medications will be defined as medications that (1) started before the first dose of study drug and were continuing at the time of the first dose of study drug, or (2) started on or after the date of the first dose of study drug up to 28 days after the subject's last dose. All medications will be presented in subject data listings.

A medication that cannot be determined as prior/concomitant/post-treatment due to missing/incomplete dates will be regarded as a concomitant medication. The summary of prior and concomitant medications will be summarized respectively. All medications will be presented in subject data listings.

5.2.6 Treatment Compliance

Subjects with treatment related protocol deviations/violations will be summarized by treatment group.

5.3 Data Analysis General Considerations

5.3.1 Pooling of Centers

This study is a multicenter study. Subjects from all centers will be pooled for all analyses.

5.3.2 Adjustments for Covariates

Not applicable.

5.3.3 Multiple Comparisons/Multiplicity

Not applicable.

5.3.4 Examination of Subgroups

No subgroup analyses are planned for this study.

5.3.5 Handling of Missing Data, Dropouts, and Outliers

In general, missing data including dates will be treated as missing and no data imputation will be applied, unless otherwise specified.

5.3.6 Other Considerations

Not applicable.

5.4 Efficacy Analyses

The primary efficacy analyses (ORR) for Phase 2 will be performed at the time of data cutoff, ie, when all subjects have discontinued the treatment or completed at least 6 months of treatment.

ORR, DOR, PFS, and CBR will be summarized descriptively on the FAS for Phase 2. Endpoints related to tumor assessments will be based on investigator assessments.

5.4.1 Primary Efficacy Analyses

Objective response rate (ORR) is defined as the proportion of subjects achieving the best overall response (BOR) of CR or PR as per RECIST 1.1 (Eisenhauer, et al., 2009). Confirmed response will be used. Subjects who do not have a clinical response assessment for any reason will be considered non-responders and will be included in the denominator when calculating the response rate.

ORR and the corresponding 90% confidence interval (CI) will be estimated and summarized for each histology type. Simon's two stage design will be used within each histology type. The following hypothesis will be tested at a one-sided 5% significance level:

$$H_0: p \leq 30\% \quad \text{Vs} \quad H_a: p \geq 55\%.$$

The first stage will enroll 9 subjects. A futility analysis will be performed when the data for the 9 subjects is available. If there are 2 or less responders (CR or PR) among the 9 subjects, the enrollment in this histology type will be stopped. If there are 3 or more responders (CR or PR), the enrollment will continue to be up to approximately 25 subjects in the second stage. If there are 12 or more responders out of 25 subjects, the null hypothesis will be rejected.

Efficacy endpoints of tumor assessment and tumor response will be presented in subject data listings.

Duration of response (DOR) will be calculated for responders and summarized descriptively using Kaplan-Meier method.

5.4.2 Secondary Efficacy Analyses

Progression-Free Survival

Progression-free survival (PFS) is defined as the time from the first study dose date to the date of disease progression (PD) as determined by investigator review or death (whichever occurs first). If a subject has not experienced PD or death, then the subject's data will be censored at the date of the last adequate radiologic assessment.

The PFS censoring rules in this SAP and definition of progression date follow the Food and Drug Administration (FDA) "Guidance for Industry Clinical Trial Endpoints for the Approval of Cancer Drugs and Biologics (2007)".

Table 2 Censoring Rules for Progression-free Survival Endpoint

Situation	End Date	Censored
Investigator documented PD	Date of the first assessment of the series of radiologic tests that determined PD	No
Death during the study before first PD	Date of death	No
No baseline or post baseline tumor assessments	Date of first dose	Yes
No progression and no death at the time of data cutoff	Date of last adequate tumor assessment* prior to data cutoff	Yes
Nonstudy anticancer treatment initiated before progression or death	Date of last adequate tumor assessment* prior to or on date of nonstudy anticancer treatment	Yes
Death or progression after more than one missed tumor assessments	Date of last adequate tumor assessment* prior to missed tumor assessments	Yes

PD = progressive disease.

* Adequate tumor assessment is radiologic assessment at regular interval as defined in the protocol.

Data cutoff generally refers to the data scope at each analysis (e.g., dry run or final analysis), from an executed cutoff or as of the final study data.

The distribution of PFS and time curve will be estimated using Kaplan–Meier method ([Kaplan and Meier, 1958](#)). Median survival time and the corresponding 90% CI will be estimated using Kaplan–Meier method for each histology type. PFS will also be graphically summarized by Kaplan–Meier curves for each histology type.

Clinical Benefit Rate

Clinical benefit rate (CBR) defined as the number of subjects with best overall response (BOR) of CR, PR, or durable SD based on RECIST 1.1, divided by the number of subjects in FAS, and corresponding confidence interval will be calculated. Durable SD is defined as SD with duration of more than 11 weeks.

The count and percentage of subjects with clinical benefit as well as exact 90% CI for the CBR will be summarized for each histology type.

5.4.3 Other Efficacy Analyses

No other efficacy analyses are planned for this study.

5.5 Pharmacokinetic, Pharmacodynamic, Pharmacogenomic, and Other Biomarker Analyses

5.5.1 Pharmacokinetic Analyses

PK analysis will be based on PK Analysis Set.

Phase 1:

Blood samples will be collected for PK analysis of both irinotecan (and its metabolite, SN-38) and eribulin as follows:

For subjects ≥ 12 months of age and > 10 kg:

- Cycle 1, Day 1: At the end of the irinotecan infusion (irinotecan is administered first), and at the end of the eribulin infusion, then at 1, 2, 4, 6, and 24 hours post-eribulin infusion. Both irinotecan (and its metabolite, SN-38) and eribulin will be assayed.
- At 72 and 120 hours post-eribulin infusion, eribulin only will be assayed.

Please note that eribulin will be administered immediately after the end of irinotecan infusion and PK blood sample draw.

Subjects < 12 months of age as well as those ≥ 12 months of age and ≤ 10 kg (subjects under 6 kg will not have PK samples taken):

- Cycle 1, Day 1: At the end of the irinotecan infusion (irinotecan is administered first) and then immediately after the end of the eribulin infusion (ie, 10 ± 5 minutes from the start of the eribulin infusion).
- Cycle 1, Day 4 or 5: During the collection of the first twice weekly CBC sample.
- Cycle 1, Day 8: Before the eribulin infusion and then immediately after the end of the eribulin infusion (ie, 10 ± 5 minutes from the start of the eribulin infusion).

Please note that eribulin will be administered immediately after the end of irinotecan infusion and PK blood sample draw.

Plasma concentrations of eribulin, irinotecan and its active metabolite SN-38 will be tabulated and summarized by dose level, day and time. PK parameters for eribulin, irinotecan, and SN-38 will be derived from plasma concentrations by noncompartmental analysis using actual times. Minimally, the following PK parameters will be calculated: maximum observed plasma concentration (C_{max}), time of maximum observed concentration following drug administration (t_{max}), area under the concentration-time curve (AUC).

Phase 2:

Eribulin will be assessed on Cycle 1 Day 1 (at the end of infusion, 0.5 to 6 hours and 24 to 120 hours after eribulin infusion) and on Cycle 1 Day 8 (pre-dose of eribulin and at the end of the infusion).

The Phase 2 PK data will be assessed using a PopPK approach. A population PK model for eribulin will be developed using non-linear mixed effect modelling. The model will be parameterized in terms of clearance and volume of distribution.

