9.7.1.7 Pharmacokinetic, Pharmacodynamic, Pharmacogenomic, and Other Biomarker Analyses

9.7.1.7.1 PHARMACOKINETIC ANALYSES

Plasma concentrations of eribulin, irinotecan and its active metabolite SN-38 will be tabulated and summarized by dose level, day and time. For Phase 1, PK parameters for eribulin, irinotecan and SN-38 will be derived from plasma concentrations by noncompartmental analysis using actual times. Minimally, the following PK parameters will be calculated: maximum observed plasma concentration (C_{max}), time of maximum observed concentration following drug administration (t_{max}), area under the concentration-time curve (AUC).

In Phase 1 the PK of both drugs (eribulin and irinotecan) will be assessed on C1D1 and in Phase 2 eribulin will be assessed on C1D1 and C1D8. The Phase 2 PK data will be assessed using a PopPK approach, pooled with Phase 1 data. A population PK model for eribulin will be developed using non-linear mixed effect modelling. The model will be parameterized in terms of clearance and volume of distribution parameters.

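### SAP 5.5.1 applies noncompartmental Cmax, tmax and AUC to sparsely sampled Phase 1 children as well, although their schedule cannot support AUC or tmax, and it omits the protocol's pooling into the population model

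*SAP*

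**What the plan says.** SAP 5.5.1 sets out two Phase 1 schedules.

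- **Full schedule** (12 months or older and over 10 kg): end of the irinotecan infusion, end of the eribulin infusion, "then at 1, 2, 4, 6, and 24 hours post-eribulin infusion", and later "At 72 and 120 hours post-eribulin infusion, eribulin only will be assayed".
- **Sparse schedule** ("Subjects < 12 months of age as well as those ≥ 12 months of age and ≤ 10 kg"; none below 6 kg): two Day 1 samples, at the end of irinotecan and 10 ± 5 minutes after the start of eribulin; then "Cycle 1, Day 4 or 5: During the collection of the first twice weekly CBC sample"; then one sample before and one after the Day 8 eribulin infusion.

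One rule follows for Phase 1 as a whole. Parameters for all three analytes "will be derived from plasma concentrations by noncompartmental analysis using actual times". On content it says: "Minimally, the following PK parameters will be calculated: maximum observed plasma concentration", followed by tmax and AUC. SAP 5.5.1 gives no restriction by schedule, minimum number of samples, AUC interval or trapezoid rule. The PK Analysis Set (SAP 5.2.1) needs only one quantifiable post-dose concentration, so sparse-schedule children qualify.

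On the population model the two documents differ. Protocol 9.7.1.7.1: "The Phase 2 PK data will be assessed using a PopPK approach, pooled with Phase 1 data". The protocol synopsis says the same in substance. SAP 5.5.1: "The Phase 2 PK data will be assessed using a PopPK approach", with no mention of Phase 1 data. The only population model named is for eribulin.

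**The concern.** A noncompartmental AUC joins the observed concentrations and measures the area beneath. It needs samples where the curve bends. The full schedule puts five samples between 1 and 24 hours after eribulin; the sparse schedule has none there, so a single segment spans the end of infusion to Day 4 or 5. If concentrations first fall quickly, that segment lies above the true curve and the AUC comes out too high.

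For irinotecan and SN-38 the difficulty is one of definition. Infants receive Schedule A only, with irinotecan daily on Days 1-5. Their Day 4/5 sample reflects several doses and is tied to a blood-count draw, not to that day's infusion.

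Comparing the PK profile with historical data is a secondary objective of both phases. Protocol 9.4.4 notes that eribulin had not been tested in infants and that CYP3A4 is immature at that age. An AUC inflated by the sampling times could be read as reduced clearance.

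**Working it through.** The documents give no AUC, half-life or error for this point, so there is no planned figure to reproduce.

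**Step 1: count the samples.**

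| | Full | Sparse |
|---|---|---|
| Eribulin, first dose | 8 (end of infusion, 1, 2, 4, 6, 24, 72, 120 h) | 3 (about 10 min, about 72-96 h, about 168 h pre-dose) |
| Irinotecan and SN-38, first dose | 7 (two end-of-infusion draws, 1, 2, 4, 6, 24 h) | 2 before redosing on Schedule A, minutes apart |

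Phase 2 eribulin sampling, which goes to the population model, has five points, including one at 0.5-6 h and one at 24-120 h. The Phase 1 sparse schedule has nothing in the earlier of those windows, yet is assigned to noncompartmental analysis.

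**Step 2: eribulin.** Assumptions, none of them in the documents: noise-free decline C(t) = (1 − f)·2^(−t/a) + f·2^(−t/b), with C = 1 at the end of infusion; slow-phase share f 5-30%; fast half-life a 0.25-2 h; terminal half-life b 24-60 h. Sparse samples are placed at 0, 84 (midpoint of 72 and 96) and 168 h.

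- True AUC(0-T) = (1 − f)·a/ln 2·(1 − 2^(−T/a)) + f·b/ln 2·(1 − 2^(−T/b))
- Linear segment = Δt·(C1 + C2)/2
- Log segment = Δt·(C1 − C2)/ln(C1/C2)

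Worked case: f = 0.10, a = 0.5 h, b = 40 h.

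- C(84) = 0.10·2^(−2.1) = 0.02333; C(168) = 0.10·2^(−4.2) = 0.00544.
- True AUC(0-168) = 0.9·0.5/0.6931 + 0.1·40/0.6931·(1 − 0.0544) = 0.65 + 5.46 = 6.11.
- Linear: 84·(1 + 0.02333)/2 + 84·(0.02333 + 0.00544)/2 = 42.98 + 1.21 = 44.19. Ratio 44.19/6.11 = 7.2.
- Log: 84·0.97667/3.758 + 84·0.01789/1.456 = 21.83 + 1.03 = 22.86. Ratio 22.86/6.11 = 3.7.

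Over the assumed ranges, estimated AUC divided by true AUC is:

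| Schedule | Linear | Log |
|---|---|---|
| Sparse, two-phase | 2.2 to 20.6 | 1.7 to 7.6 |
| Full (0-120 h), two-phase | 1.02 to 1.21 | 1.00 to 1.09 |
| Sparse, one-phase, half-life 60 down to 24 h | 1.08 to 1.45 | 1.00 |

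Sensitivity: with a 5-minute infusion, samples at 10 minutes, 72 h and 168 h, slow-phase share down to 2% and terminal half-life down to 10 h, the sparse ratios are 1.9 to 40 linear (median 6.8) and 1.5 to 9.4 with log-down (median 2.8). The full schedule gives 1.02 to 1.37 and 1.00 to 1.09.

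**Step 3: irinotecan, Schedule A.** Assumed half-lives 0.25-1 h and 3-12 h, slow-phase share 10-100%, Day 4 sample taken pre-dose.

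- Against the true multi-dose AUC over 0-72 h: 1.0 to 6.7 linear (median 2.5), 0.9 to 2.2 log-down (median 1.4).
- Against the single-dose AUC over 0-24 h: 3.7 to 20 linear, 2.9 to 7.5 log-down.
- If the Day 4 sample falls at the end of infusion: 1.8 to 14 against AUC 0-72.5 h.

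The answer changes with the interval and with when the blood count is drawn; the SAP fixes neither.

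**The case against.** **The group may be nearly empty.** Protocol 9.4.4, in text added by Amendment 6 after Phase 1 was complete, says eribulin had not been tested in this infant group. That suggests, without proving, that few or no infants were dosed in Phase 1. Phase 2 infants fall under the population-model rule, and children under 6 kg give no samples. What remains may be a few Phase 1 children aged 12 months or more and weighing 6-10 kg. This stands.

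**The documents do not show a wrong AUC being reported.** A reader might infer that these children's AUCs will be wrong several-fold. The plan does not support that: the ratios need assumed two-phase kinetics, and one-phase decline with the log rule gives none of the error. SAP 9 keeps derivation rules in separate documents, where a minimum-sample rule could sit. This also stands, though no such rule is visible in the SAP.

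**Other analyses remain.** A reader might also infer that noncompartmental analysis is all these children get, or that the SAP revoked pooling. Neither follows. SAP 5.5.1 also tabulates concentrations by dose level, day and time; SAP 3.1.3 keeps the model-derived exposure objective; and Protocol 9.7.1 leaves further detail to the SAP. The pooling is omitted, not withdrawn.

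**Some parameters are sound.** Both drugs are infused and sampled at the end of infusion, so Cmax of eribulin and irinotecan is observable. This is right, and the fix keeps it.

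**The consequence is limited.** PK is secondary, data under 12 months are descriptive only, and the SAP already names the selected Phase 2 dose. This stands, except that the descriptive-only note does not cover children of 12 months or more weighing 10 kg or less.

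**Conclusion.** The point holds as a defect in the written rule. SAP 5.5.1 requires noncompartmental AUC and tmax from a schedule that cannot support them. For irinotecan and SN-38 on Schedule A this follows from the dosing and sampling days alone: no single-dose AUC is defined, and tmax can only be one of the times sampled. SN-38 Cmax has the same weakness, since a metabolite need not peak at the end of the parent's infusion.

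For eribulin the size is conditional. Under the assumed two-phase kinetics the AUC could be about 1.7 to 20 times the true value; it is unbiased if decline is one-phase and the log rule applies. These figures show what could happen, not what will. The full schedule stays within about 21% with the linear rule under the same assumptions, so the weakness lies in the sparse sampling.

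Practical weight is modest: a secondary endpoint and an unstated, possibly very small, number of children. The change is still worth making, because the sponsor's protocol already plans a better method for eribulin.

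**What to change.** In SAP 5.5.1:

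1. Limit noncompartmental AUC and tmax for all three analytes, and SN-38 Cmax, to subjects on the full schedule (12 months or older and over 10 kg).
2. For sparse-schedule subjects, report concentrations by nominal time and the observed end-of-infusion concentration as Cmax for eribulin and irinotecan.
3. Restore the protocol's pooling of Phase 1 data, so that sparse-schedule eribulin samples enter the population model with the full Phase 1 profiles and exposure is estimated from it.

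If the separate programming specifications already contain a minimum-sample rule for AUC, the SAP should state it.

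The cost is SAP wording only: no new samples, and the eribulin population model is already planned. The downside is that no irinotecan or SN-38 AUC will be reported for sparse-schedule children.

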5.5.2 Pharmacokinetic Analyses and Pharmacodynamic Analyses

Exploratory/graphical analysis will be conducted for PK/pharmacodynamic evaluations, ie, dose and/or exposure effect relationships will be explored for the effects of eribulin mesilate on tumor responses as determined by RECIST 1.1 (CR, PR and SD), PFS and ORR, as well as AEs/dose reductions, and may be followed by model-based analysis. Further details will be documented separately.

5.5.3 Pharmacodynamic, Pharmacogenomic, and Other Biomarker Analyses

Not applicable.

5.6 Safety Analyses

The primary endpoint for Phase 1, the incidence of DLTs, will be summarized by dose level for the DES using frequency and percentage. All other evaluation of safety will be performed on the Safety Analysis Set. Safety data that will be evaluated include adverse events, clinical laboratory results, ECG, vital signs, and Karnofsky/Lansky performance status score.

Descriptive summary statistics (e.g., n, mean, standard deviation, median, 25th percentile (Q1), 75th percentile (Q3), minimum, and maximum for continuous variables; n [%] for categorical variables) of clinical laboratory test results, vital signs measurements, ECG parameters, and changes from baseline will be presented.

5.6.1 Extent of Exposure

Descriptive summary statistics will be presented for the number of cycles/weeks on treatment, total dose (mg/m²) per subject, actual dose intensity (mg/m²/week) per subject, and relative dose intensity per subject.

Duration of treatment (weeks), dose intensity (mg/m²/week), and relative dose intensity (%) will be calculated as the following:

$$\text{Duration of treatment (weeks)} = (\text{date of first dose of last cycle} + 21 - \text{date of first dose of study drug}) / 7.$$

$$\text{Actual Dose intensity (mg/m}^2\text{/week)} = \text{Total dose (mg/m}^2\text{)} / \text{Duration of treatment (weeks)}$$

$$\text{Relative dose intensity (\%)} = \text{Actual Dose intensity} / \text{Planned dose intensity} \times 100.$$

The number of subjects with study drug dose reduction, treatment interruption, and discontinuation due to adverse events will be summarized.

5.6.2 Dose Limiting Toxicities

The primary objective for phase 1 is to determine MTD and RP2D. The MTD is defined as the highest dose level at which less than 1/3 of subjects experience a DLT during Cycle 1 of therapy. The MTD will be determined based on the incidence of DLTs in Cycle 1 of each dose level.

MTDs will be obtained for both Schedule A and Schedule B and the most appropriate schedule will be taken forward to Phase 2 and will represent the RP2D (See Section 9.4.1 in the protocol for details on schedule selection).

The primary endpoint for Phase 1, ie, the incidence of DLTs will be summarized by dose level for the Dose Evaluable Set (DES) using frequency and percentage.

5.6.3 Adverse Events

The AE verbatim descriptions (investigator terms from the CRF) will be classified into standardized medical terminology using the Medical Dictionary for Regulatory Activities (MedDRA). Adverse events will be coded to the MedDRA (Version 22.0 or higher) lower level term (LLT) closest to the verbatim term. The linked MedDRA preferred term (PT) and primary system organ class (SOC) are also captured in the database.

A treatment-emergent adverse event (TEAE) is defined as an AE that emerges during treatment, having been absent at pretreatment, or

- Reemerges during treatment, having been present at pre-treatment (Baseline) but stopped before treatment, or
- Worsens in severity during treatment relative to the pretreatment state, when the AE was continuous.

Only those AEs that are treatment-emergent will be included in summary tables. All AEs, treatment-emergent or otherwise, will be presented in subject data listings.

The incidence of TEAEs will be reported as the number (percentage) of subjects with TEAEs by SOC and PT. A subject will be counted only once within an SOC and PT, even if the subject experienced more than 1 TEAE within a specific SOC and PT. The number (percentage) of subjects with TEAEs will also be summarized by highest CTCAE grade (CTCAE v5.0).

The number (percentage) of subjects with treatment-related TEAEs will also be summarized.

The number (percentage) of subjects with treatment-emergent serious adverse events (SAEs) will be summarized by MedDRA SOC and PT. A subject data listing of all SAEs will be provided.

The number (percentage) of subjects with TEAEs of fatal outcome will be summarized by MedDRA SOC and PT. A subject data listing of all AEs with fatal outcome will be provided.

The number (percentage) of subjects with TEAEs leading to discontinuation from study drug will be summarized by MedDRA SOC and PT. A subject data listing of all AEs leading to discontinuation from study drug will be provided.

